## **11.1. Endpoints**

### **11.1.1. Primary Endpoints**

- Adverse events, collected until the 42-day post-last vaccination (excluding third vaccination) visit.
- Serious adverse events and IREs, collected from signing of the ICF onwards until the end of the study.
- Solicited local and systemic adverse events (reactogenicity), collected until 7 days after each study vaccine administration.

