## PROTOCOL AMENDMENTS

Protocol Version	Issue Date
Original Protocol	30 March 2015
Amendment 1	26 June 2015
Amendment 2	9 September 2016
Amendment 3	4 May 2017

Amendments below are listed beginning with the most recent amendment.

---

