#### TITLE PAGE

**Amendment\_2 (9 September 2016)**

This amendment is considered to be substantial based on the criteria set forth in Article 10(a) of Directive 2001/20/EC of the European Parliament and the Council of the European Union.

**The overall reason for the amendment:** This amendment includes the request of the Center for Biologics Evaluation and Research (CBER, a division of United States [US] Food and Drug Administration [FDA]) to change the age ranges of Cohorts 3 and 4 and to extend the safety follow-up to 6 months post-boost. The latter request was originally made for other VAC52150 protocols and has now also been implemented for this protocol. The sponsor halted vaccinations following a case of Miller Fisher syndrome after receipt of MVA-BN-Filo or placebo in a clinical study. This interruption continued until a revised informed consent form (ICF) containing updated safety language for the current study VAC52150EBL2002 was prepared and approval to restart the study was granted by the relevant competent authority. As a result of the pause, some subjects will be outside the protocol-defined boost vaccination window. Information was added to clarify the procedures that need to be followed for these subjects. Based on the request of the Agence Nationale de Sécurité du Médicament et des produits de santé (ANSM) for study VAC52150EBL2001, the sponsor has decided to implement the collection of neurologic and autoimmune events (“Immediate Reportable Events”) throughout the entire clinical development plan.

The changes made to the clinical protocol VAC52150EBL2002 Amendment 1 (dated 26 June 2015) are listed below, including the rationale of each change and a list of all applicable sections.

---

**Rationale:** As requested by the CBER (US FDA), the age ranges of Cohort 3 and Cohort 4 have been changed to 4 to 11 years (Cohort 3) and 1 to 3 years (Cohort 4) to align with World Health Organization (WHO)-defined age cohorts which effectively increases the number of subjects aged 1 to 3 years. Since this age group has a different immune response to vaccination than older children and adults, the increased sample size of Cohort 4 will provide deeper understanding of the immunogenicity of the vaccine.

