## 5 TREATMENT ALLOCATION AND BLINDING

[11.7 Interim Analyses](#)

---

**Rationale:** As requested by the ANSM, wording on the collection of “Immediate Reportable Events” was added after one subject in study VAC52150EBL2001 experienced a serious and very rare condition called “Miller Fisher syndrome” about a month after boost vaccination with either MVA-BN-Filo or placebo.

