In a substudy at selected sites, approximately 90 healthy adult subjects in Cohort 1 (Groups 1 and 2) will receive a third vaccination with Ad26.ZEBOV at  $5 \times 10^{10}$  vp or placebo at least 1 year post prime vaccination. Subjects who received Ad26.ZEBOV and MVA-BN-Filo will receive Ad26.ZEBOV as third vaccination. Subjects who received placebo will receive placebo as third vaccination.

The study consists of a screening phase of up to 8 weeks (starting from the moment the subject signs the informed consent form [ICF] and/or assent), a vaccination phase in which subjects will be vaccinated at baseline (Day 1) followed by a boost vaccination on Day 29, 57 or 85, a post-vaccination phase and long-term follow-up phase until Day 365. The Cohort 1 substudy consists of a vaccination phase in which subjects will be vaccinated at least 1 year post prime vaccination, a post-vaccination phase, and a long-term follow-up phase until the 1-year post third vaccination visit. All subjects within a cohort will be followed in a blinded manner by the site until the last subject in that cohort has completed the study. Any subject who completed either the 6-month post-prime and/or the Day 365 visit prior to approval of Amendment 2 was required to attend the 6-month post-boost and the Day 365 visit after approval of Amendment 2.

While Cohort 1 was enrolling, the sponsor halted all vaccinations in this study due to the occurrence of a serious and very rare condition, Miller Fisher syndrome, reported in study VAC52150EBL2001, until a revised ICF was prepared and approval to restart the study was granted by the relevant competent authority. This interruption in dosing affected over 200 consented subjects, some who were awaiting prime vaccination and some awaiting boost vaccination. When approval was granted to restart the study under Amendment 1, a late boost vaccination has been offered to those subjects who were out-of-window

for the boost vaccination, unless it was prohibited. Those subjects who agreed to the late boost have been following the procedures as outlined in Amendment 1.

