The final analysis will be performed when all subjects have completed the last study-related visit or discontinued earlier (including subjects participating in the Cohort 1 substudy).

While Cohort 1 was enrolling, the sponsor halted all vaccinations in this study due to the occurrence of a serious and very rare condition, Miller Fisher syndrome, reported in study VAC52150EBL2001 (described in Section 1.1.2.3) until a revised ICF was prepared and approval to restart the study was granted by the relevant competent authority. This interruption in dosing affected over 200 consented subjects, some who were awaiting prime vaccination and

some awaiting boost vaccination. When approval was granted to restart the study under Amendment 1, a late boost vaccination has been offered to those subjects who were out-of-window for the boost vaccination, unless it was prohibited. Those subjects who agreed to the late boost have been following the procedures as outlined in Amendment 1.

All subjects (including placebo) who were primed prior to the pause and did not/will not receive a late boost vaccination are being followed every 3 months after the prime vaccination for safety until Day 365 (see [Additional Time and Events Schedule](#) for subjects who do not receive a boost vaccination because of a study pause). Therefore, non-serious adverse events will be reported until the 42-day post-last vaccination (excluding third vaccination) visit rather than the 42-day post-boost vaccination visit. Serious adverse events and IREs will be reported throughout the study until Day 365 (for details, see Section [9.3.1](#)).

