7.1.3. Analysis Methods

In general, the AEs following vaccination will be summarized (ie, tables of descriptive statistics) by vaccination schedule and presented per period/phase. Similar summary tables will also be provided pooled by vaccine (dose).

Furthermore, unsolicited AEs will be summarized (showing number and percentage) by System Organ Class (SOC) and Preferred Term (PT). Solicited AEs (recorded by day) will be converted into the analysis format of unsolicited AEs (recorded by event) as detailed in Attachment 2. These solicited AEs will be summarized by class (local, systemic) and Preferred Term. For solicited as well as unsolicited AEs, tables focusing on severity will be created. Focus will also be on the relationship (to the study vaccine) of the solicited systemic and unsolicited AEs.

The SAEs, AEs with fatal outcome, AEs leading to permanent discontinuation from study vaccination, Grade 3 AEs and IREs will also be listed. A table summarizing all those parameters will further be created and presented per analysis period and vaccination schedule. Summary tabulations by SOC and PT for each of the category of events (ie, SAEs, AEs with fatal outcome, AEs leading to permanent discontinuation from boost vaccination, Grade 3 AEs and immediate reportable events) will also be generated on the entire reporting period. Subject narratives will be generated for these events, except Grade 3 AEs. For Grade 3 AEs, the narratives will only be generated for those AEs that are considered related to study vaccination.

For the solicited local and systemic AEs, the duration and time to first onset of the events will also be summarized. If a subject experiences more than 1 occurrence of a solicited event, the maximum duration of the events will be used. The time to first onset is defined as:

$$[\text{date of first onset} - \text{reference date} + 1]$$

The reference date is the start date of each vaccination period (ie, Post-dose 1, Post-dose 2 or Post-dose 3). Duration and time to onset of AEs will be expressed in days.

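### Dedicated IRE collection began with Amendment 2, after part of Cohort 1 had been vaccinated, yet the SAP pools IREs from consent as if ascertainment were uniform

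*Protocol*

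**What the plan says.** Protocol 11.1.1 gives one window for the whole event class: "Serious adverse events and IREs, collected from signing of the ICF onwards until the end of the study". SAP Section 7 uses the same start and end. SAP 7.1.3 plans a summary table of IREs and other selected events by analysis period and schedule, and also "Summary tabulations by SOC and PT for each of the category of events", IREs included, over the full reporting period. SAP 2.4 presents safety by cohort and schedule. None of these sections mentions the protocol version under which follow-up took place. SAP Section 3, on changes to the planned analysis, deals only with the immunogenicity and per protocol sets.

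The Amendment 2 history, dated "9 September 2016", states that "the sponsor has decided to implement the collection of neurologic and autoimmune events". Its rationale adds that the IRE wording "was added after one subject in study VAC52150EBL2001 experienced a serious and very rare condition". On the state of this trial, Protocol 3.1 says: "While Cohort 1 was enrolling, the sponsor halted all vaccinations in this study". The Synopsis reports: "This interruption in dosing affected over 200 consented subjects, some who were awaiting prime vaccination and some awaiting boost vaccination". Both place the resumption of dosing before Amendment 2: "When approval was granted to restart the study under Amendment 1", out-of-window subjects were offered a late boost, and those who accepted followed Amendment 1 procedures.

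**The concern.** An endpoint window that opens at consent presumes that the collection procedure existed at consent. For Cohort 1 subjects primed before Amendment 2 took effect, dedicated IRE collection did not. If early follow-up enters the IRE table on the same footing as later follow-up, time without dedicated collection is counted as event-free and the percentage may be too low.

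This matters because a neuroinflammatory case led to the pause, and because Protocol Section 11 says the primary analysis, on Cohort 1, will help choose the schedule to take forward. SAP 2.3 gives the pause its own sensitivity analysis for immune response. The event class behind the pause has no counterpart on the safety side.

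**Working it through.** The plan states no figure on this point to reproduce. The check is one of sequence, then of which events and comparisons are exposed.

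**Sequence.**
- Amendment 1 is dated 26 June 2015 and Amendment 2 "9 September 2016" (Protocol Amendments). IRE collection enters with Amendment 2. The history is used here only to date a procedure; a difference between it and the current text is not an error.
- Current text (Synopsis and 3.1) has Cohort 1 enrolling at the halt, then a restart under Amendment 1.
- Protocol 3.1 provides for subjects who had completed the 6-month post-prime or Day 365 visit before Amendment 2 was approved. The plan therefore contemplates long follow-up ahead of that amendment.

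**Which events are exposed.** Protocol 9.3.1 collects all adverse events to 42 days after the last vaccination (third vaccination excluded), then only SAEs and IREs. Before IREs were a category, the later period had SAEs alone. Two types of event are left:
1. Non-serious IREs starting after the 42-day visit and before Amendment 2.
2. Events recorded as AEs or SAEs that fit the 12.1.1 list but were never put on an IRE form.

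For a subject boosted on schedule, the all-AE window ends at nominal Day 71, 99 or 127 in Groups 1, 2 and 3. The first type of gap can then span at most 365 − 71 = 294, 365 − 99 = 266 or 365 − 127 = 238 days to Day 365. These are ceilings. They differ because of the boost day, not the enrolment date, and do not apply to late-boosted or unboosted subjects.

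**Which comparisons are exposed.** Under Protocol 3.1 and Table 1, Cohort 1 enrols 3 × 132 = 396 subjects at 1:1:1, then 264 at 1:1 to Groups 1 and 2, giving 264/264/132. All of Group 3, but only 132/264 = 50% of Groups 1 and 2, comes from the first phase.

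Suppose true IRE rates are equal, capture is d for subjects enrolled before some cut and 1 afterwards, and e1 and e3 are the shares of Groups 1 and 3 enrolled before the cut. The observed Group 3 to Group 1 ratio is

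(1 − (1 − d)·e3) / (1 − (1 − d)·e1).

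Both d and the cut are assumptions, because the documents give neither.

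| Cut at 396 enrolled (e3 = 1, e1 = 0.5) | Ratio |
|---|---|
| d = 0.9 | 0.90/0.95 = 0.95 |
| d = 0.75 | 0.75/0.875 = 0.86 |
| d = 0.5 | 0.50/0.75 = 0.67 |
| d = 0.25 | 0.25/0.625 = 0.40 |

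With d = 0.5 and the cut at 132, 264, 396, 528 or 660 enrolled, the ratio is 0.91, 0.80, 0.67, 0.80 or 1.00. If all 660 enrolled before the cut, this between-schedule distortion vanishes, but under-capture in absolute terms remains.

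Groups 1 and 2 enrol concurrently throughout, so their ratio is 1.00 at any cut and any d. Active and placebo are allocated 5:1 within every group, so that contrast is also unaffected by enrolment timing.

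**The case against.** The strongest reply is that the possible gap is narrow and the visible text offers other routes. All adverse events were collected to the 42-day visit. Serious IREs go through SAE reporting (12.1.1). Subjects were told to contact the investigator about later illness (Time and Events Schedule, note d). Subjects who had passed the 6-month post-prime or Day 365 visit had to attend again after Amendment 2. The triggering case in the other study was serious and arose about a month after boost, so it would have been caught on both counts. SAP 7.1.3 lists every IRE and plans a narrative for each, and its main safety periods end at relative Day 29, inside the all-AE window. The study is descriptive, with no hypothesis test. All of this stands. It narrows the exposed events and means that interpretation, not error rates, is affected. It does not make ascertainment uniform.

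Protocol Section 12.3.3, which covers IRE reporting, is not in the text available for review and may hold a retrospective rule. A reader might infer that these events had no collection route at all; that cannot be asserted.

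A reader might also infer that all of Cohort 1 was vaccinated before Amendment 2. No passage says so, and the Synopsis has some subjects still awaiting prime at the halt. Nor do the documents support a general claim that IRE rates by schedule and cohort reflect enrolment date: two of the main contrasts are protected, and enrolment dates for Cohorts 2a, 2b and 3 are not given. Finally, the zero-event limits in Protocol 11.2 are a general planning statement and claim nothing about IRE ascertainment.

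**Conclusion.** The point holds in limited form. For the part of Cohort 1 vaccinated before Amendment 2 took effect, dedicated IRE collection from consent was not possible prospectively, and the SAP neither says so nor allows for it. IRE percentages in those subjects may be biased low, chiefly for late-onset non-serious events. Group 3 versus Groups 1 and 2, and Cohort 1 versus later cohorts, could be affected, depending on enrolment dates the documents do not give.

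No size can be fixed for this trial. The ratios above illustrate a model in which capture depends only on whether enrolment fell before or after the cut. A share of follow-up lost, computed from an assumed Amendment 2 day, would likewise not be evidence about this trial. The conclusion also assumes that Section 12.3.3 contains no retrospective rule that closes the gap.

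**What to change.** In SAP 7.1.3:
1. Apply the Protocol 12.1.1 IRE list as a fixed MedDRA term search to all AEs and SAEs in the database, whatever protocol version was in force, and tabulate the matches alongside form-reported IREs. The paresthesia item needs the recorded dates as well as the term, because the list sets a minimum duration.
2. Split the entire-period IRE table into follow-up before and after Amendment 2 took effect at the site, with person-time for each part. The search cannot recover events that were never recorded, so the split is needed too.

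In SAP Section 3, state when IRE collection began, and cite any retrospective rule in Protocol 12.3.3. Protocol 11.1.1 can stay as it is; changing a primary endpoint would need a formal amendment and is not required.

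The cost is a term list, one date per site, one extra table and a smaller stated IRE exposure. Trial conduct does not change.

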### **11.1.2. Secondary Endpoint**

#### *Humoral immune response*

- Binding antibody levels elicited by vaccination using EBOV GP ELISA at 21 days post boost.

#### *Safety and tolerability (Cohort 1 substudy)*

- Adverse events, collected from the day of the third vaccination onwards until 28 days thereafter (note: events that started before the third vaccination but are still present at the time of third vaccination should also be recorded).
- Serious adverse events and IREs, collected from signing of the original ICF onwards until the end of the study (including Cohort 1 substudy).

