## DEFINITIONS OF TERMS

Study vaccine	Ad26.ZEBOV, MVA-BN-Filo or placebo.
Blinded study vaccine administrator	A blinded trained study nurse, medical doctor, or otherwise qualified health care provider.
Independent study vaccine monitor	An unblinded study vaccine monitor assigned to the study who is responsible for the unblinded interface between the sponsor and the investigational site pharmacy.
Solicited adverse events (reactogenicity)	Local and systemic adverse events that are common and known to occur after vaccination and that are usually collected in a standard, systematic format in vaccine clinical studies. For the list of solicited adverse events in this study, see Section 9.3. For the purpose of vaccine clinical studies, all other adverse events are considered unsolicited; however, this definition should be distinguished from definitions based on pharmacovigilance guidelines.
End of the study (for a subject)	For subjects in the Cohort 1 substudy: after completion of all assessments at the 1-year post third vaccination visit. For all other subjects: after completion of all assessments at the 6-month post-boost vaccination visit or at the Day 365 visit, whichever occurs later.

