#### **Secondary Objectives**

The secondary objectives are:

- To assess humoral immune responses, as measured by ELISA, to the EBOV GP at 21 days post boost of different vaccination schedules of Ad26.ZEBOV and MVA-BN-Filo administered IM as heterologous prime-boost regimens on Days 1 and 29, Days 1 and 57, or Days 1 and 85, in healthy adults, including elderly subjects, and on Days 1 and 29 and Days 1 and 57 in HIV-infected subjects and healthy children in 2 age strata.
- To assess the safety and tolerability of a third vaccination with Ad26.ZEBOV administered at least 1 year post prime in a subset of approximately 90 healthy adults, including elderly subjects, in Cohort 1 (Groups 1 and 2).

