## 6.3. Contraindications to Boost and Third Vaccinations

A subject will not be given the boost or third vaccination if he or she experiences any of the following events at any time after the prime or boost vaccination, respectively:

1. Anaphylaxis clearly attributable to vaccination with study vaccine; *OR*
2. Generalized urticaria within 72 hours of vaccination considered to be at least possibly related to study vaccine; *OR*
3. A serious adverse event considered to be at least possibly related to study vaccine; *OR*
4. Injection site ulceration, abscess or necrosis considered to be at least possibly related to the study vaccine; *OR*
5. Any other safety concern threatening the subject's safety or persisting clinically significant abnormality considered to be related to prime vaccination.

Subjects experiencing any of the events described above must not receive any further study vaccine, but should be monitored for safety and for immunogenicity according to the protocol as described in Section 10.2.

An ad hoc IDMC meeting may be requested via the sponsor for any single event or combination of multiple events which are considered to jeopardize the safety of the subjects.

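### The third-dose SAE/IRE endpoint starts at main-study consent, and neither the primary SAE/IRE endpoint, the dedicated SOC/PT tables nor the Post-dose 2 follow-up phase stops at Dose 3

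*Protocol*

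**What the plan says.** The secondary objective in Protocol 2.1 is "To assess the safety and tolerability of a third vaccination with Ad26.ZEBOV administered at least 1 year post prime". Protocol 11.1.2 gives that objective two safety endpoints with different starting points. The AE endpoint is "Adverse events, collected from the day of the third vaccination onwards until 28 days thereafter". The SAE/IRE endpoint is "Serious adverse events and IREs, collected from signing of the original ICF onwards until the end of the study (including Cohort 1 substudy".

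The primary endpoints in Protocol 11.1.1 differ from each other in the same way. The AE endpoint is "Adverse events, collected until the 42-day post-last vaccination (excluding third vaccination) visit". The SAE/IRE endpoint is "Serious adverse events and IREs, collected from signing of the ICF onwards until the end of the study", with no exclusion of the third vaccination. The Definitions of Terms fix when the study ends: "For subjects in the Cohort 1 substudy: after completion of all assessments at the 1-year post third vaccination visit".

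On analysis, SAP 7 repeats a single SAE/IRE window from consent to end of study. SAP 7.1.3 says that the SOC/PT tabulations of SAEs, fatal AEs, AEs leading to permanent discontinuation, Grade 3 AEs and IREs "will also be generated on the entire reporting period". It also plans one table of these categories by analysis period and schedule, and listings. SAP Table 2 defines a Post-dose 3 period and a Post-dose 3 follow-up phase. It ends Post-dose 1 and its follow-up one minute before Dose 2, but gives Post-dose 2 and its follow-up no corresponding end before Dose 3.

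**The concern.** Two questions need separate answers: how safe the two-dose schedules are, and how safe the third Ad26.ZEBOV dose is. As worded, each SAE/IRE endpoint takes in events that belong to the other.

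For the third dose, events from screening, after prime and after boost count, although they arose a year or more before Dose 3 or in the months leading up to it. That earlier time is also selected. Protocol 6.3 bars further vaccination after "A serious adverse event considered to be at least possibly related to study vaccine", and a subject who died cannot receive Dose 3. The pre-dose time is therefore largely free of related and fatal events by construction, while unrelated earlier SAEs still count.

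For the two-dose schedules, events after an extra dose enter the results of Groups 1 and 2. Group 3 has no substudy. Attribution to the right dose matters here because the programme was paused over a single neurological case. With about 75 active substudy subjects, one misplaced event is 1/75 = 1.3%.

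**Working it through.** The plan states no figure on this point, so there is none to reproduce. The check compares the windows and then does person-time arithmetic.

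**Inputs**
- Dose 3 at 12 to 15 months after prime, with 12 months of follow-up after it: Protocol Table 6.
- About 90 substudy subjects: Protocol Table 2.
- Groups 1 and 2: 264 each, 528 in total, of whom 440 are active: Protocol Table 1.
- Main-study follow-up of about 1 year per subject, and screening of 0 to 56 days.
- Assumptions: no dropout; non-substudy follow-up ends at about Day 365; and, where active subjects are counted, 5:1 allocation holds in the substudy, giving 90 × 5/6 = 75 active.

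**1. Share of the third-dose SAE/IRE window that precedes Dose 3**
- Dose 3 at 12 months: 12/(12 + 12) = 50%.
- Dose 3 at 15 months: 15/(15 + 12) = 56%.
- Counting from consent with 56 days of screening and Dose 3 on Day 456: (56 + 456)/(56 + 456 + 364) = 512/876 = 58%.

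**2. Share of the primary SAE/IRE window in Groups 1 and 2 that follows Dose 3**
- All subjects, Dose 3 at 12 months: 90 × 1 = 90 person-years; 90/(528 + 90) = 14.6%.
- All subjects, Dose 3 at 15 months: the wait adds 90 × 0.25 = 22.5 person-years of true two-dose time; 90/(528 + 22.5 + 90) = 14.1%.
- Active only, upper end: 75 × 364/(440 × 365 + 75 × 364) = 27,300/187,900 = 14.5%.
- Active only, lower end (56 days of screening, Dose 3 on Day 456): 27,300/(440 × 421 + 75 × 91 + 27,300) = 27,300/219,365 = 12.4%.

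**3. Post-dose 2 follow-up phase in SAP Table 2**

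Post-dose 2 ends on relative Day 29, so its follow-up starts on study Day 58 in Group 1 and Day 86 in Group 2. As written, it runs to last contact.

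| Group | Dose 3 day | Days as written | Days if cut at Dose 3 | Share after Dose 3 |
|---|---|---|---|---|
| 1 | 365 | 672 | 307 | 54% |
| 1 | 456 | 763 | 398 | 48% |
| 2 | 365 | 644 | 279 | 57% |
| 2 | 456 | 735 | 370 | 50% |

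The Post-dose 2 period itself closes well before Dose 3, so the missing stop has practical effect in the follow-up phase.

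**4. Two events traced through the rules**
- An unrelated SAE ten days after prime in a later substudy subject meets the primary endpoint and also the third-dose endpoint.
- An SAE 60 days after Dose 3 in a Group 1 subject meets both endpoints and appears in the entire-period SOC/PT table under the 28-day schedule. SAP Attachment 1 allocates by whether onset falls within a period's limits, so it fits both Post-dose 2 follow-up and Post-dose 3 follow-up.

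Attachment 1 names only Post-dose 1 and Post-dose 2 as active periods in its allocation and combination rules, so it does not resolve the double fit. The Regimen phase pools all three doses (Table 2, Note 1).

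**The case against.** The strongest reply is that the endpoint text describes collection, and that the SAP governs analysis. Post-dose 3 begins at the date and time of Dose 3, has its own follow-up phase, and is named as a focus in SAP 7, which analyses only subjects who received the dose. SAP 7.1.3 plans a per-period table of SAEs, fatal AEs, discontinuations, Grade 3 AEs and IREs, with listings, and narratives for all but unrelated Grade 3 AEs. Protocol 11.5 also promises separate summaries for third-dose subjects.

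Much of this stands. A reader might infer that the plan yields no third-dose SAE result at all, or that the entire-period tables are the only SOC/PT tables to show SAEs. The documents do not support either reading. Unsolicited AEs are tabulated by SOC and PT, AE tables are generally given per period, and SAEs are not excluded from them. SAEs in the 28 days after Dose 3 can therefore be seen separately.

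A reader might also infer 17% to 21% extra follow-up in Groups 1 and 2 against none in Group 3. The 17% is 90/528; the 21% is 112.5/528 and counts the wait before Dose 3, which is genuine two-dose time. Group 3 is unclear: footnote c of the main Time and Events Schedule follows every subject for SAEs and IREs until the last subject in the cohort completes, while the Definitions of Terms end a non-substudy subject's study at Day 365 or 6 months post-boost, whichever is later.

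Finally, no formal schedule comparison is planned, and the primary analysis is triggered by the 6-month post-boost visit. How many post-Dose-3 events it would contain depends on calendar dates that the documents do not give.

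The reply does not dispose of the point, because the per-period table relies on Table 2, where Post-dose 2 follow-up runs on through Dose 3.

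**Conclusion.** The point holds as a defect of windows and table periods that the SAP only partly repairs. About half (50% to 56%) of the post-prime time in the third-dose SAE/IRE endpoint precedes Dose 3. About 90 person-years after Dose 3, roughly 15% of the Groups 1 and 2 total (12% to 15% of active time if 5:1 holds), fall inside the primary SAE/IRE endpoint. Some 48% to 57% of a substudy subject's Post-dose 2 follow-up, as written, lies after Dose 3. No SOC/PT table dedicated to SAEs and IREs is planned for the third dose.

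These shares assume the planned numbers, no dropout, and about one year of follow-up outside the substudy. If footnote c governs, non-substudy follow-up is longer and the 15% is smaller. The secure difference between Groups 1 and 2 and Group 3 is the extra dose, not the length of follow-up. The summaries are counts and percentages of subjects, so the person-time shares show exposure to misallocation and are not a bias estimate. It would go too far to say that two-dose and three-dose safety cannot be told apart: the per-period outputs separate them in part.

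**What to change.** Leave data collection unchanged and amend the analysis text.

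1. Protocol 11.1.2 and SAP 7: analyse the substudy SAE/IRE endpoint from the date and time of the third vaccination.
2. SAP Table 2: add an end one minute before Dose 3 to Post-dose 2 and to Post-dose 2 follow-up. In SAP Attachment 1, name Post-dose 3 as an active period.
3. SAP 7.1.3: for substudy subjects, end the main-study SOC/PT tables of SAEs, fatal AEs, Grade 3 AEs and IREs by schedule one minute before Dose 3. Add a separate SOC/PT table of the same categories from Dose 3 to the end of the substudy.

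The cost is one extra set of tables and a few lines of text. Vaccination and event dates are already recorded, so sites have nothing further to do.
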